The study employs a multi-stage cluster sampling method. In the first stage, one central urban area (tentatively identified as Dongcheng Street, which oversees 31 primary schools) and one non-central urban area (tentatively identified as Gaobu Town, which oversees 13 primary schools) will be randomly selected, reflecting the urban-rural structure of Dongguan City. In the second stage, ten primary schools will be randomly selected from each administrative district, with five designated as intervention group schools and the remaining five as control group schools. This results in a total of twenty primary schools, evenly split between the intervention and

control groups. In the third stage, two classes from each of the two grades (fourth and fifth grades) are randomly selected from each of the twenty selected schools using a cluster sampling method, with surveys conducted at the class level. Each school comprises a minimum of 152 students. Schools with 152 students will have one additional class randomly selected. The final estimated total sample size is projected to be 3036. Random sampling and randomized grouping are achieved using computer software to generate random numbers. The sample size is determined using the following formula:

$$n = \frac{\left\{ z_{1-\alpha/2} \sqrt{2(m-1)\rho + 2} + z_{\beta} \sqrt{m\rho + 1} \right\}^2 * \{p_1(1-p_1) + p_2(1-p_2)\}}{(p_1 - p_2)^2}$$

where: n is the desired sample size for each cohort, $z_{1-\alpha/2}$ is the value corresponding to the accepted Type I error rate (eg $z_{1-\alpha/2}$ about 1.96 for an error rate of 0.05), z_{β} is the value corresponding to the desired statistical power, e.g., for a power of 0.8, z_{β} is approximately 0.84. m is the size of each cohort, ρ is the intra-group correlation coefficient, p_1 is the expected outcome rate in the test group (ie, influenza vaccination rate), and p_2 is the expected outcome rate in the control group. Based on the assumption that the anticipated influenza vaccination rate is 80% in the intervention group and 50% in the control group, the estimated sample size, denoted as 'n', is 138 students per school.^{13, 14} This implies that approximately 138 primary school students are required for each group, yielding a total sample size of 2760 individuals. To account for potential sample attrition, the sample size is expanded by 10%, resulting in a final estimated total sample size of 3036 for statistical analysis.

Intervention methods

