The intervention group will receive a health education intervention focused on

influenza vaccination literacy, while the control group will continue with their standard school health education without any additional intervention. An influenza vaccination health education including topics such as the importance of influenza vaccination, benefits of vaccination, and vaccination methods, will be developed and reviewed by an expert group. The package for the intervention group will include educational activities, distribution of promotional materials, vaccination services, and distribution of vaccination souvenirs. The details are as follows:

1) Educational activities include classroom lectures and parent meetings. Medical professionals or public health experts will be invited to deliver lectures at the school, providing detailed information on the role and benefits of influenza vaccination and the risks of influenza. Teachers and relevant school staff will be trained to understand the importance of influenza vaccination, reinforcing these messages in everyday teaching. Content about influenza vaccines will be incorporated into school health education courses, facilitating student learning about influenza vaccines. In addition, Teachers will discuss the importance of the flu vaccine at parent meetings, encouraging parents to facilitate their children's vaccination.

2) Promotional materials include educational booklet, animated videos, vaccination service and vaccination souvenirs. Educational booklet will be designed and distribute to students to raise their awareness of flu vaccines. Animated videos will be created to explain the effects of flu vaccines and the benefits of vaccination in an easy-to-understand manner. These videos will be played on school TVs or computers, and students will be organized to watch them. Influenza vaccination services will be provided to students who have no contraindications to influenza vaccination, are in

good health, and are 4-6 months post their last influenza vaccination, based on the principle of informed consent, voluntariness, and self-payment. 'Epidemic Prevention Little Guards' medals will be created and distributed to vaccinated students as a commemorative incentive to encourage vaccination.

Intervention time

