Staff of the affiliated street Center for Disease Prevention and Control (CDC) will visit the school in the first month to implement intervention activities using the health education intervention package. The intervention period will commence in September 2023 and conclude in February 2024, resulting in a total intervention duration of approximately three to four months. The specific intervention process is as follows: 1) At the start of the semester (early intervention stage in September 2023), initiation activities will be conducted. The investigators will introduce the study to teachers and students, and medical professionals or public health experts will be invited to deliver classroom lectures at the intervention group schools. Baseline data will be collected at this stage. 2) During the intervention period (September 2023 – January 2024), the intervention group will follow the health education intervention toolkit to conduct intervention activities. 3) At the conclusion of the semester (February 2024), follow-up data will be collected. The intervention timeline is shown in the Figure 2.

Data collection and analysis

Questionnaire surveys will be administered to students and parents before and after

the intervention, using self-completion. The questionnaire design, which is informed by similar research literature (Appendix 1 & 2), will undergo evaluations for reliability and validity. The questionnaire will include the following content: 1) Socio-demographic characteristics (name, age, sex, class, residential address, parents' educational level, occupation, family income); 2) Personal history (basic disease history, allergy history, and personal history); 3) Influenza vaccination health literacy level. The health literacy level concerning influenza vaccination will be assessed across four dimensions: knowledge, attitude, behavior, and skills related to influenza vaccination. Details of these four dimensions include knowledge of basic facts about the influenza vaccine (such as its efficacy, vaccination frequency, and side effects), attitudes towards the influenza vaccine (including perceptions of its efficacy and safety), behavioral characteristics related to influenza vaccination (such as willingness to be vaccinated, vaccination status, and timing of vaccination), and sources of information about the influenza vaccine.

Confirmation of influenza and surveillance of influenza-like cases

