organizational process and division of responsibilities. Their primary responsibilities include: on-site inspection of various investigation and evaluation operational processes, immediate correction of identified issues; on-site review and re-testing of collected information, with rectification based on re-test results; collection, summarization, and analysis of investigation and evaluation quality control issues, with timely reporting and sharing of these issues.

Patient and public involvement

Students and their parents, teachers, and/or the public were not involved in the design, or conduct, or reporting, or dissemination plans of this study.

ETHICS AND DISSEMINATION

This study follows the Declaration of Helsinki and the Chinese clinical trial research ethics and regulations. Before the commencement of the project, ethical approval has been sought from the Ethics Committee of the School of Public Health, Sun Yat-sen University. The research process respects the autonomy of students and schools. The primary schools selected for this study have an equal probability of being assigned to either the intervention or control group, ensuring the impartiality and fairness of the research. Prior to the initiation of the study, the lead researcher provided an overview of the study's purpose, procedures, and potential risks. Comprehensive informed consent forms, detailing the study's intent, processes, and potential risks, will be handed to both students and their guardians, and participation is strictly voluntary. Data confidentiality is ensured through anonymization and restricted access, with only the core study team able to view raw data. Provisions are also in place to address any adverse reactions or events related to the study or vaccination.

Findings from the study will be made accessible to both the scientific community and the public. Results are slated for submission to peer-reviewed journals, ensuring validation and broader reach within the research community. Beyond academic circles, outcomes will be relayed to key stakeholders, including school officials, health departments, and community leaders, fostering informed decisions at the grassroots level. Additionally, feedback sessions, online postings, and conference presentations are avenues being considered to ensure widespread dissemination and awareness.

Funding: This work was supported by the Department of Education of Guangdong Province (grant number: 51000-42240006).

REFERENCES

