Appendix

Appendix I Health Literacy Research Questionnaire (Parent Version)

Appendix II Health Literacy Research Questionnaire (Student Version)

Appendix III Registration Form of Influenza-like Cases in the School Clinic

Appendix IV SPIRIT 2013 Checklist

**Appendix I Questionnaire for the Health Literacy Study of Influenza Vaccination
among Primary School Students in Dongguan City (Parent Version)**

Question

Basic information

The street where your child's school belong is?

Your child's school?

Your child's ID type?

Your child's ID number?

Your phone number?

Are you the child's father, mother or?

Do you currently live with your children?

Your age?

Your spouse's age?

Your highest level of education?

Your spouse's highest level of education?

Your occupation?

Your spouse's occupation?

Your home address?

Your household income?

How many children do you currently have?

How is your child's health?

Knowledge questions

Do you know what the symptoms of flu are?

Do you know when is the flu season in Dongguan?

Do you know how the flu is transmitted?

Do you think the flu is an infectious disease?

Do you know what the flu vaccine is?

Have you heard of the flu vaccine?

Do you know the minimum age for children to receive their first

flu vaccination?

Do you think it's appropriate to get the flu vaccine during a flu epidemic?

Do you know the contraindications of flu vaccination?

Do you know what the possible side effects of the flu vaccine are?

Attitude Questions

Do you think the flu is just a cold?

Do you think you need to be quarantined at home after getting the flu?

Do you think your family and friends are likely to get the flu during the pandemic season?

If you or your child gets the flu, there is a high risk of transmitting it to others around you?

Do you think that getting the flu can cause serious consequences or complications?

If you or a family member gets the flu, it can have a serious impact on your or your family's health?

Do you think the flu vaccination is the most effective preventive measure against influenza?

Do you think the flu vaccination is effective in reducing the risk of spreading the influenza virus?

Do you think the flu vaccination will reduce the risk of your family getting the flu?

Do you think the flu vaccination will reduce the symptoms of influenza in your family?

Do you think children are a priority and recommended population for the flu vaccination?

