Do you think the flu vaccine needs to be given every year to

prevent the flu?

Do you think getting a flu vaccine is good for you and your child's health?

Do you think it is necessary to get a flu vaccine?

Are you confident that the flu vaccine is safe?

Behavioral questions

Within the last year, have you ever had influenza (or had a sudden onset of illness with a high fever $\geq 38^{\circ}\text{C}$ accompanied by flu-like symptoms such as generalised malaise, myalgia, sore throat, etc.)?

If yes, when was the last time you had influenza (or had a sudden onset of illness with high fever $\geq 38^{\circ}\text{C}$ accompanied by influenza-like symptoms such as generalised malaise, myalgia, sore throat, etc.)?

Has your child had influenza (or had a sudden onset of illness with high fever $\geq 38^{\circ}\text{C}$, accompanied by flu-like symptoms such as generalised weakness, myalgia, sore throat, etc.) within the last year?

If yes, when was the last time your child had influenza (or had a sudden onset of illness with a high fever $\geq 38^{\circ}\text{C}$ accompanied by influenza-like symptoms such as generalised malaise, myalgia and sore throat)?

Have you taken your child for a flu vaccination between 2020 and 2022?

Have you or your spouse been vaccinated against flu in 2023?

If you have been vaccinated against flu, when did you or your spouse get the flu vaccine this year?

Has your child been vaccinated against flu in 2023?

If your child has been vaccinated against flu, when did your

child get the flu vaccine this year?

If your child has been vaccinated against flu, why did you decide to take your child for a flu vaccination this year?

If your child hasn't been vaccinated against flu, why did you decide not to take your child for a flu vaccination this year?

If your child has not had a flu vaccination this year, are you currently willing to take your child to get one?

Would you be willing to take your child for a flu vaccination in the future?

Would you like to recommend that others get the flu vaccine?

Skill Questions

Do you know how to schedule your flu vaccine?

Do you take an active interest in information about flu vaccinations?

Where do you get information about flu vaccinations?

Appendix II Questionnaire for Health Literacy Study of Influenza Vaccination among Primary School Students in Dongguan City (Student Version)

Question

Basic information

Your class?

Your gender?

How old are you?

knowledge questions

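### The primary vaccination rate has no named data source and appears to rest on unblinded, unverified self-report, with only the intervention arm under added pressure to report vaccination

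*Combined protocol and SAP*

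**What the plan says.** Study outcomes defines the vaccination rate, one of two primary outcomes, as the vaccinated count over the total. It names no data source.

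Data collection and analysis has students and parents answer questionnaires before and after "the intervention, using self-completion", and lists vaccination status and timing among the behavioural content. In Appendix I the parent item is "Has your child been vaccinated against flu in 2023", followed by a question on when. Appendix II puts the equivalent items to the pupil. Neither form asks for a card, certificate or other record. The parent form does ask for "Your child's ID number".

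Under Intervention methods, the intervention arm receives lectures, teacher reinforcement, parent meetings that urge vaccination, a self-paid vaccination service, and this: "medals will be created and distributed to vaccinated students as a commemorative incentive to encourage vaccination". Controls keep routine health education and receive nothing extra. No blinding is described, and SPIRIT item 17a in Appendix IV is marked N/A.

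Quality control includes "on-site review and re-testing of collected information, with rectification based on re-test results", in general terms and without mention of vaccination records. The municipal CDC surveillance network is named as a source for influenza cases, not for vaccination.

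**The concern.** Respondents know their arm. In one arm, school staff and health professionals spend months presenting vaccination as the desirable act; in the other they add nothing to routine teaching. Asked by the same study whether the child was vaccinated, some intervention families may say yes when the answer is no. Over-reporting that is equal in the two arms largely cancels in a comparison near the null. Over-reporting that is more common in the intervention arm does not, and it pushes the result towards benefit.

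Two outcomes are exposed. The primary vaccination difference would be inflated. The vaccine protection rate, which compares influenza incidence in vaccinated and unvaccinated pupils, would count some unvaccinated pupils as vaccinated. A larger sample or a cluster-adjusted test would correct neither.

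The plan is also stricter with a secondary outcome than with this primary one: confirmed influenza needs a positive pathogen test, while vaccination has no confirmation rule.

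**Working it through.** **Inputs from the plan (Sampling method).** 138 pupils per school, 20 schools split 10 and 10, and "anticipated influenza vaccination rate is 80% in the intervention group and 50% in the control group". The normal quantile is "about 1.96 for an error rate of 0.05".

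**The plan's own figure.** 138 × 20 = 2760, or 1380 per arm, and 2760 × 1.10 = 3036, as stated. The 138 itself cannot be confirmed, because the cluster size m and the intra-cluster correlation ρ have no values. With ρ = 0 the printed formula gives (1.96√2 + 0.84)² × (0.16 + 0.25)/0.30² = 59.4, so 60. The point below does not depend on this.

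**Bias in the primary outcome.** Let p be the true rate in both arms, and f₁ and f₀ the net fractions of unvaccinated pupils reported as vaccinated in the intervention and control arms. The documents give no misreporting rate, so f is an assumption.

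Spurious difference = (1 − p)(f₁ − f₀). With p = 0.50 and f₀ = 0 this is 0.5 f₁:

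- f₁ = 5%: 2.5 points
- f₁ = 10%: 5 points
- f₁ = 20%: 10 points
- the whole 30-point design difference: f₁ = 0.30/0.50 = 60%

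If the true rates were the planned 80% and 50%, only 20% of intervention pupils could be falsely reported. The same f₁ would then add 0.20 f₁, that is 1, 2 or 4 points.

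**Would it reach significance?** Under independence, SE = √(2 × 0.25/1380) = 1.9 points, so the threshold is 1.96 × 1.9 = 3.7 points and a 5-point bias gives z = 5/1.9 = 2.6. Allowing for clustering, the variance is multiplied by 1 + 137 × ICC: 2.37 at an assumed ICC of 0.01 and 7.85 at 0.05.

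| Variance | SE (points) | z for 5 points | Chance of p < 0.05 at f₁ = 5%, 10%, 20% |
|---|---|---|---|
| Independence | 1.9 | 2.6 | 26%, 75%, >99% |
| ICC 0.01 | 2.9 | 1.7 | 14%, 40%, 93% |
| ICC 0.05 | 5.3 | 0.9 | 8%, 16%, 47% |

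Clustering widens the interval; the bias stays where it is.

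**Exposure in the vaccine protection rate.** In the intervention arm with p = 0.50 and f₁ = 10%, the reported vaccinated share is 0.50 + 0.05 = 0.55, of whom 0.05/0.55 = 9.1% are unvaccinated. If they have the same influenza risk as other unvaccinated pupils, the protection rate estimated in that arm is 1 − 0.091 = 0.909 times its true value.

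**The case against.** Five points on the other side carry weight.

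1. **The plan never says the outcome is questionnaire-based.** True. That is an inference from the absence of any other described source, and Figures 1 and 2 could not be read here. If records are intended, the plan should say so.
2. **The medal is part of the intervention.** A reader might infer that medals lead families to report vaccinations that did not happen. The documents do not support that: no text ties a medal to a questionnaire answer, no medal is offered to parents, and real uptake prompted by a medal is a proper effect. The supportable concern is the general pressure of the package, combined with unverified answers.
3. **A z of 2.6 looks decisive.** It needs an assumed 10% false-report rate, none in controls, and independent pupils. The plan lists a chi-square test without stating a unit, while the Introduction makes schools the unit of analysis. With clustering allowed for, z is about 1.7 or 0.9 at the assumed ICCs.
4. **There are partial safeguards.** Both parent and pupil are asked, with dates; the questionnaires are to be evaluated for reliability and validity; quality control re-checks data. These help, but parent and pupil answer under the same pressure, no rule covers disagreement, and none of these steps is described as a check against a record.
5. **CDC staff could check status.** They are described as visiting in the first month to deliver the intervention. Nothing shows them available in control schools or at the February 2024 follow-up.

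A reader might also infer that no analysis could repair the damage. That goes too far: a verified sample in each arm, or a later match on the ID number, would allow a correction. What remains after all five is that the source is unnamed and no verification is planned.

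**Conclusion.** The point holds as a gap in outcome definition and ascertainment. Followed as written, the plan leaves a primary outcome open to over-reporting that differs by arm, in the direction of benefit, and lets the same error into the vaccine protection rate.

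The size cannot be known from the documents. The 2.5 to 10 points rest on no true effect, 50% vaccinated, accurate control reports and net false reporting of 5% to 20%. Over-reporting equal in both arms would give no spurious difference under these null assumptions. A reader might infer that misreporting could account for the entire anticipated effect. That would need 60% of unvaccinated intervention pupils to be falsely reported, and nothing in the documents suggests it. The realistic risk is a modest effect created or enlarged. The change should be made; it is not a reason to consider the trial uninterpretable.

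**What to change.** In Study outcomes and in Data collection and analysis:

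- Define the primary outcome as vaccination within a stated study window, supported by a dated record obtained in the same way in both arms. Suitable sources are a card or certificate photo added to the parent questionnaire, or a match on the child's ID number where available. The printed items ask about 2023 while follow-up is in February 2024, so the window needs explicit dates.
- Do not use the school-service roster as a source. The service is described only for the intervention arm. A roster would document vaccinations there automatically while control families must find a card, which would itself bias towards benefit.
- Report record availability by arm. Do not simply count a missing record as unvaccinated without a sensitivity analysis of that choice. Keep self-report as a sensitivity analysis.
- If full checking is not feasible, verify an equal random sample in each arm, spread over all schools, through the existing quality-control re-check. Report agreement by arm and correct each arm's rate: with q the reported rate, corrected rate = q × (share of reported vaccinated confirmed) + (1 − q) × (share of reported unvaccinated found to be vaccinated). In the example above, 0.55 × 0.909 + 0.45 × 0 = 0.50. Carry the uncertainty of these shares into the interval.

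The cost is one added upload or item, some extra data handling, and some missing records.
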